**Flow Diagram**

## **a. Data and Hypotheses**

Our final dataset will include the full sample of people we attempted to message, i.e., the anonymous dataset that we used for randomization along with the outcome measures from ATRI on APT Webstudy enrollment, incentive payments, and completion of both cognitive assessments.

Below we provide our main null hypotheses:

Aim 1, Primary Endpoint: Enrollment Rates

H1null: Financial incentives, certain small financial incentive or a prize opportunity incentive, will result in similar enrollment rates of CCRMC patients into the APT Webstudy relative to a message-only arm (active control).

Aim 2, H2null: A prize opportunity incentive will result in similar enrollment rate of CCRMC patients into the APT Webstudy as a certain small financial incentive with the same expected value.

- Secondary Endpoint(s): Cost per enrollee

H2null: The cost per APT Webstudy enrollee will be similar for the financial incentive arms compared with the message-only arm.

- Secondary Endpoint(s): Completion rates for both cognitive assessments

H3null: Completion rates for both cognitive assessments will be similar for the financial incentive arms compared with the message-only arm.

## **b. Sample size determination**

Data used in the power analysis are based on members ages 50 and over without MCI/Dementia currently included in the CCHS database. We power the study for the primary endpoint – enrollment rates. We based our power calculations on a two-sided chi-square test for detecting a difference between two proportions, assuming a type I error rate of 2.5% (to account for the two hypotheses of interest). With a sample size of 16,000 members in each treatment arm (48,000 overall), and assuming an enrollment rate of 2% in the active control arm, we have 90% power to detect an absolute difference of 0.59% or higher (an enrollment rate of 2.59% or higher) in either of the two financial incentive groups.

We also plan to conduct sub-group analyses, with a particular focus on racial and ethnic minorities. With sample sizes of 2100, 3600, 2940, and 5380 per arm in the Black, Asian, Latino(a) and White sub-groups, and assuming the same 2% enrollment rate in the active control arm, we have 90% power to detect an enrollment rate of 1.8%, 1.34%, 1.5% and 1.07% respectively in either of the two financial incentive arms. The sample size also provides adequate power to detect meaningful differences in other pre-specified populations of interest (based on primary language (English/Spanish), and age group (50-64, 65-74, 75 and over).

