## 2. Purpose/Objectives/Aims/Research Questions

Primary Objectives: To assess the impact of offering financial incentives (a certain small financial incentive or a randomized prize incentive) on enrollment rates of a population of diverse low-income adults ages 50 years and older into the APT Webstudy.

Secondary Objectives: To test whether the prize incentive is more effective at increasing enrollment than the certain small financial incentive. To assess the impact of financial incentives on cost per enrollee and, separately, completion of two cognitive assessments.

Tertiary Objectives: To analyze all primary and secondary outcomes for the following subgroup characteristics at baseline: sex (M/F), race and ethnic groups (Latino/Hispanic, non-Hispanic White, non-

Hispanic Black, non-Hispanic Asian, Other), primary language (English/Spanish), message modality (email or text) and age group (50-64, 65-74, 75 and over).

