### **c. Statistical Analysis**

The primary analysis will be based on the intention-to-treat (ITT) population of all messaged patients who are empaneled at Contra Costa Regional Medical Center (CCRMC), who are ages 50 and older and have no prior documentation of dementia.

Participant demographics and characteristics at time of messaging will be summarized for each intervention arm, using frequencies and percentages for categorical variables, and using mean, standard deviation, and quartiles for continuous variables. Comparisons across the three intervention groups will be done using a Chi-square test for categorical variables and an analysis of variance (ANOVA) test for continuous variables with Fisher's Exact Test or Dunnett's post-hoc tests, for categorical and continuous data respectively, to compare each active intervention arm against the control arm.

Our primary outcome is the enrollment status at 2-weeks. A multivariable logistic regression analysis will be performed to study the association between enrollment status and intervention arms (financial incentive arms vs active control arm) adjusting for age group (50-64, 65 and over), race and ethnic status (Latino/Hispanic, non-Hispanic White, non-Hispanic Black, non-Hispanic Asian, Other) and message modality (email or text). Separate analyses will be conducted for each financial incentive intervention arm against the active control arm.

All results will be reported as point estimates (e.g., percentage difference between groups) and interval estimates (two-sided 95% confidence intervals). All hypothesis tests to test group differences between each of the active intervention arms and the active control arm will be conducted at a two-sided alpha level of 0.025.

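### The race/ethnicity subgroup detectable effects are absolute increases mislabelled as enrollment rates; as written, all four lie below the 2% control rate and the 90% power does not hold

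*Protocol*

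**What the plan says.** Section 5b of the protocol (Sample size determination) bases power on a "two-sided chi-square test for detecting a difference between two proportions". Alpha is set at 2.5% per comparison because each incentive arm is tested against control. For the whole sample the section takes 16,000 per arm and a 2% control rate, and gives the result in both forms: "we have 90% power to detect an absolute difference of 0.59% or higher (an enrollment rate of 2.59% or higher").

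The next paragraph turns to the racial and ethnic subgroups. It gives 2100, 3600, 2940 and 5380 per arm for the Black, Asian, Latino(a) and White groups, and it keeps the control rate: "assuming the same 2% enrollment rate in the active control arm". The power claim that follows for the four groups is this: "we have 90% power to detect an enrollment rate of 1.8%, 1.34%, 1.5% and 1.07% respectively in either of the two financial incentive arms".

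The Tertiary Objectives in section 2 include race and ethnic group among the subgroup analyses: "To analyze all primary and secondary outcomes for the following subgroup characteristics at baseline". Section 5c confirms that tests of each incentive arm against control "will be conducted at a two-sided alpha level of 0.025".

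**The concern.** Each of the four stated enrollment rates is lower than the control rate given in the same sentence. The trial asks whether incentives raise enrollment, so an incentive-arm rate of 1.07% to 1.8% against 2% cannot be the intended target. The stated power also cannot be uniform on that reading: the Black subgroup, the smallest, would have the same 90% power for a gap of 0.2 points as the White subgroup, the largest, for a gap of 0.93 points.

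The protocol says these subgroups are a particular focus, and this sentence is the only place where their power is quantified. A reader who takes the figures at face value gets the wrong size and the wrong direction of effect. A reader who sees only that they are small may think that modest subgroup effects are detectable. Both errors matter when a null subgroup result is interpreted.

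**Working it through.** **Inputs** (section 5b unless noted): two-sided chi-square test for two proportions; alpha 0.025, so z = 2.2414; 90% power, so z = 1.2816; control rate c = 0.02; equal arms (1:1:1 allocation, section 5); n per arm 2100, 3600, 2940 and 5380.

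**Formula.** For incentive-arm rate t, let d = |t − c| and p = (c + t)/2. Then

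- SE0 = √[2p(1 − p)/n]
- SE1 = √{[c(1 − c) + t(1 − t)]/n}
- power = Φ[(d − 2.2414 × SE0)/SE1]
- n per arm for 90% power = {2.2414√[2p(1 − p)] + 1.2816√[c(1 − c) + t(1 − t)]}² / d²

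**Step 1: reproduce the overall figure.** With n = 16,000 and t = 0.0259, d = 0.0059, SE0 = 0.001674 and SE1 = 0.001674. Power = Φ[(0.0059 − 2.2414 × 0.001674)/0.001674] = Φ(1.283) = 90.0%. The required n is 15,988 per arm. The protocol's overall statement is correct, and the formula matches the one it used.

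**Step 2: the subgroup sentence as written** (t equal to the stated rate).

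| Subgroup | n per arm | t | Gap from 2% (points) | Power | n per arm for 90% |
|---|---|---|---|---|---|
| Black | 2100 | 1.80% | −0.20 | 3.9% (4.2% counting both tails) | 115,664 |
| Asian | 3600 | 1.34% | −0.66 | 47.8% | 9,356 |
| Latino(a) | 2940 | 1.50% | −0.50 | 21.8% | 17,070 |
| White | 5380 | 1.07% | −0.93 | 95.4% | 4,336 |

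Example, Black: SE0 = 0.004213 and SE1 = 0.004213, so power = Φ[(0.002 − 2.2414 × 0.004213)/0.004213] = Φ(−1.767) = 3.9%.

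Other conventions do not rescue this reading. A one-sided 0.025 test (the same as two-sided 0.05) gives 6.9%, 58.9%, 30.9% and 97.5%. A continuity correction gives 3.0%, 44.1%, 19.0% and 94.6%.

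**Step 3: the same figures as absolute increases** (t = 2% plus the stated figure).

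| Subgroup | t | Power | n per arm for 90% (stated n) | Exact increase at 90% power (points) | Relative increase |
|---|---|---|---|---|---|
| Black | 3.80% | 89.2% | 2156 (2100) | 1.83 | 1.8/2 = 90% |
| Asian | 3.34% | 90.1% | 3591 (3600) | 1.34 | 1.34/2 = 67% |
| Latino(a) | 3.50% | 89.9% | 2949 (2940) | 1.50 | 1.5/2 = 75% |
| White | 3.07% | 90.1% | 5355 (5380) | 1.07 | 1.07/2 = 54% |

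Example, Black: d = 0.018, SE0 = 0.005179 and SE1 = 0.005171, so power = Φ[(0.018 − 2.2414 × 0.005179)/0.005171] = Φ(1.236) = 89.2%.

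All four figures come within one point of 90% power at four different sample sizes. For comparison, the relative increase detectable in the whole sample is 0.59/2 = about 30%.

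**The case against.** The strongest reply is that this is a slip of wording and not a power deficit. The paragraph before gives the same kind of result in both forms, the sentence restates the 2% control rate, and the values shrink as subgroup size grows, as detectable differences do. A statistician would probably recover the meaning. The trial is sized on the primary endpoint, the subgroups are a tertiary objective, and nothing in the design changes. The low literal powers describe reductions in enrollment that nobody set out to detect, so they should not be taken to mean that the subgroups are underpowered. The correction is also an inference, because the protocol never says that the four figures are increases.

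Most of this stands. Only the label is wrong, the literal powers serve only to show that the sentence cannot be right, and the sponsor should confirm the intended reading. What does not stand is that the context makes the sentence acceptable. It uses the same term for the four figures as for the 2% beside them, no other section corrects it, and a reader can confirm the meaning only by redoing the calculation. Ethics reviewers and non-statistical readers are unlikely to do that.

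**Conclusion.** The sentence is wrong as written. Against a 2% control rate, the stated enrollment rates correspond to power of about 4%, 48%, 22% and 95% (the last for a decrease), not 90%. Taken as absolute increases, they reproduce at 89.2% to 90.1%. The detectable incentive-arm rates are then about 3.8%, 3.34%, 3.5% and 3.07%: enrollment would have to rise by roughly half in the White subgroup and nearly double in the Black subgroup.

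This rests on the protocol's own test, alpha, control rate and subgroup sizes, and on the inference that differences were meant. The close agreement in all four groups makes that inference strong. The shortfall for the Black subgroup (1.8 stated, 1.83 exact) is rounding, not a second error. The primary sample size, alpha, tests and primary claim are unaffected. It should be corrected because it is the only quantified power statement for subgroups that the protocol singles out.

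**What to change.** After the sponsor confirms that differences were intended, replace the claim with wording such as: 90% power to detect an absolute increase of about 1.8, 1.34, 1.5 and 1.07 percentage points (enrollment rates of about 3.8%, 3.34%, 3.5% and 3.07%, i.e. relative increases of about 90%, 67%, 75% and 54%) in the Black, Asian, Latino(a) and White subgroups respectively, in either incentive arm. This matches the two-form presentation already used for the overall sample.

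The cost is one reworded sentence. Sample size, allocation, alpha and analysis stay as they are.

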### **c. Statistical Analysis**

The primary analysis will be based on the intention-to-treat (ITT) population of all messaged patients who are empaneled at Contra Costa Regional Medical Center (CCRMC), who are ages 50 and older and have no prior documentation of dementia.

Participant demographics and characteristics at time of messaging will be summarized for each intervention arm, using frequencies and percentages for categorical variables, and using mean, standard deviation, and quartiles for continuous variables. Comparisons across the three intervention groups will be done using a Chi-square test for categorical variables and an analysis of variance (ANOVA) test for continuous variables with Fisher's Exact Test or Dunnett's post-hoc tests, for categorical and continuous data respectively, to compare each active intervention arm against the control arm.

Our primary outcome is the enrollment status at 2-weeks. A multivariable logistic regression analysis will be performed to study the association between enrollment status and intervention arms (financial incentive arms vs active control arm) adjusting for age group (50-64, 65 and over), race and ethnic status (Latino/Hispanic, non-Hispanic White, non-Hispanic Black, non-Hispanic Asian, Other) and message modality (email or text). Separate analyses will be conducted for each financial incentive intervention arm against the active control arm.

All results will be reported as point estimates (e.g., percentage difference between groups) and interval estimates (two-sided 95% confidence intervals). All hypothesis tests to test group differences between each of the active intervention arms and the active control arm will be conducted at a two-sided alpha level of 0.025.

Our secondary outcomes are cost per enrollee and completion of both cognitive assessments in the APT Webstudy. A multivariable linear regression will be performed to study the association between the cost per enrollee and intervention arms (financial incentive arm, active control arm) adjusting for age group (50-64, 65 and over), race and ethnic status (Latino/Hispanic, non-Hispanic White, non-Hispanic Black, non-Hispanic Asian, Other) and message modality (email or text). The other secondary outcome, completion of both cognitive assessments in the APT Webstudy, will be analyzed using a multivariable logistic regression analogous to the analysis of the primary outcome. Analyses of the secondary outcomes will also be conducted at a two-sided alpha level of 0.025, without further adjustment for multiplicity.

Prespecified sub-group analyses based on age group (50-64, 65 and over), race/ethnicity (Latino/Hispanic, non-Hispanic White, non-Hispanic Black, non-Hispanic Asian, Other) and message modality (email or text) will be conducted on all primary and secondary outcomes using analogous methods to the overall analysis. In addition, if feasible with available sample size, we will analyze sub-groups at the intersection of two or more of the identities of interest, e.g., racial/ethnic groups by age-group.

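### Section 5c gives the prize-versus-$25 comparison of enrollment (Aim 2) no test or interval, and pairs 95% intervals with tests at 0.025

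*Protocol*

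**What the plan says.** **The objective.** Protocol section 2 lists as its first secondary objective: "To test whether the prize incentive is more effective at increasing enrollment than the certain small financial incentive". Section 5a places the matching null among the main hypotheses, as Aim 2: "A prize opportunity incentive will result in similar enrollment rate of CCRMC patients into the APT Webstudy as a certain small financial incentive", the two offers having equal expected value.

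**The sample size.** Section 5b powers the incentive arms against control, "assuming a type I error rate of 2.5% (to account for the two hypotheses of interest").

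**The analysis.** Section 5c models enrollment by logistic regression, with arm described as the incentive arms against control, and adds: "Separate analyses will be conducted for each financial incentive intervention arm against the active control arm". The 0.025 level is given for "All hypothesis tests to test group differences between each of the active intervention arms and the active control arm". Results are to be reported with "interval estimates (two-sided 95% confidence intervals").

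**The secondary outcomes.** Section 5c continues: "Our secondary outcomes are cost per enrollee and completion of both cognitive assessments in the APT Webstudy". Their level is set by: "Analyses of the secondary outcomes will also be conducted at a two-sided alpha level of 0.025, without further adjustment for multiplicity". The cost model again compares incentive with control, and the completion analysis follows the pattern of the primary one.

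**The concern.** Section 5c fixes models, contrasts and a significance level, but none of them covers a hypothesis that the protocol itself states. An analyst who follows 5c faithfully reports two comparisons with control and no test of prize against certain incentive. An analyst who adds the test must choose its level, possibly after the data are seen.

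The risk is that the two comparisons with control are read as the answer to Aim 2: one is significant, the other is not, so the first incentive is taken to be the better one. That inference is invalid, because a difference in significance is not a significant difference. The choice between two offers of equal expected value is a deliberate feature of the design and needs its own contrast.

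A smaller problem sits in the same section. A 95% interval and a test at 0.025 can point in different directions for the same primary contrast.

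**Working it through.** **1. Which comparison has a stated level?**

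| Comparison | Stated as objective or null | Contrast in 5c | Level in 5c |
|---|---|---|---|
| Certain incentive vs control, enrollment | yes (Aim 1) | yes | 0.025 |
| Prize vs control, enrollment | yes (Aim 1) | yes | 0.025 |
| Prize vs certain incentive, enrollment | yes (section 2; Aim 2 in 5a) | none | none |
| Cost per enrollee, completion of both assessments | yes | incentive vs control | 0.025 |

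**2. The protocol's own power figure.** Inputs from section 5b: 16,000 per arm, 2.0% vs 2.59%, two-sided 0.025. Power is Φ[(d − z·s0)/s1], where s0 is the standard error with pooled variance and s1 the one with unpooled variance.

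- Pooled rate = (0.0200 + 0.0259)/2 = 0.02295
- s0 = √(2 × 0.02295 × 0.97705/16,000) = 0.001674
- s1 = √((0.0200 × 0.9800 + 0.0259 × 0.9741)/16,000) = 0.001674
- (0.0059 − 2.241 × 0.001674)/0.001674 = 1.283, so power = 0.900

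The stated 90% reproduces. At 0.05 the power would be 0.941. The 2.5% is therefore 0.05 split over the two comparisons with control.

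**3. Can the two comparisons with control answer Aim 2?** Three arms of 16,000 were simulated with at least 1,000,000 trials per scenario, control at 2.0%, pooled two-proportion tests at 0.025 and both incentives given the same true rate. The common rates are assumptions, except 2.0% (no effect) and 2.59% (the rate in 5b).

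| Common incentive rate | Exactly one of the two tests rejects |
|---|---|
| 2.0% | 4% |
| 2.1% | 8% |
| 2.2% | 19% |
| 2.3% | 31% |
| 2.4% | 33% |
| 2.59% | 13% |
| 2.8% | 1% |
| 3.0% | about 0% |

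At common rates of 2.30% to 2.59%, the direct prize-versus-certain test is non-significant at 0.05 in 83% to 88% of the trials with a split result.

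**4. What the design can detect for Aim 2.** This uses the formula of step 2, with 16,000 per arm, 90% power and two-sided 0.025. The protocol gives no rate for the certain arm under Aim 2, so it is assumed.

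| Certain-arm rate | Detectable difference |
|---|---|
| 2.0% | 0.59 points |
| 2.59% | 0.66 points |
| 3.0% | 0.71 points |

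For 2.59% vs 3.0%, a difference of 0.41 points, the power is 49%.

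**5. Interval against test.** When the p-value lies between 0.025 and 0.05, the 95% interval from the same analysis excludes no effect but the test does not reject. The probability is the power at 0.05 minus the power at 0.025. At +0.59 points over a 2.0% control rate this is 0.941 − 0.900 = 0.041. It is 0.106 at +0.40 and 0.109 at +0.30. The 97.5% interval is wider by 2.241/1.960 = 1.14.

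**The case against.** **This is detail for the SAP.** The contrast and level of a secondary comparison are often left to it, and 5c does not forbid a further contrast. That would carry weight if 5c were silent. But 5c does specify contrasts and levels, and the ones it specifies leave out a stated aim.

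**The 0.025 for secondary analyses already applies.** This is the natural default, and the fix adopts it. It is still an inference: 5c names its secondary outcomes as cost and completion, and Aim 2 concerns enrollment.

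**An estimate is available.** This stands. A reader might infer that 5c makes any prize-versus-certain estimate impossible, but it does not. The opening description of the regression could be read as a three-arm model, and two separate analyses that share a control arm allow a point estimate by subtraction. What 5c lacks is a stated test and interval.

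**The error rate.** A reader might infer that Aim 2 breaks the control of type I error. With no effect in any arm, the chance of at least one rejection is 4.6% for the two primary tests and 6.4% if Aim 2 is added at 0.025. That matters only if Aim 2 belongs to the controlled family, which the protocol does not say. It tests its other secondary analyses without further adjustment, so doing the same for Aim 2 is no error. Nor do the documents require a gate on a primary rejection or a replacement of the primary model.

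**Intervals.** Unadjusted 95% intervals beside tests at a split level are a common choice, and decisions rest on the tests. That is fair, but the protocol does not label the intervals as unadjusted, and the mismatch is cheap to remove.

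**Conclusion.** The concern holds in a limited form. Aim 2 is a stated objective with its own null, and section 5c followed as written yields neither a test nor an interval for it.

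The two comparisons with control cannot fill the gap. How often they split when the incentives are equally effective depends strongly on the common rate: near one third at 2.4%, but 4% at 2.0% and 1% at 2.8%. A reader might take the high values as a general risk; they hold only at the assumed rates shown. The harm also requires that someone misreads a split result, which the protocol does not itself do.

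The mismatch between interval and test affects about 4% of trials per primary contrast at the planned effect of +0.59 points, and about 11% at +0.30 to +0.40.

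All figures assume 16,000 per arm, a 2.0% control rate and unadjusted two-proportion tests in place of the covariate-adjusted logistic model. The stated power for the comparisons with control is not in question here.

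**What to change.** 1. Leave the primary analyses unchanged. Add to section 5c a prize-versus-certain contrast on enrollment for Aim 2, by logistic regression with the same covariates (age group, race and ethnic status, message modality). Make it a secondary test at two-sided 0.025 without further adjustment, as 5c does for the other secondary analyses, and report it with a 97.5% interval.
2. State its detectable difference in section 5b: about 0.59 to 0.71 points at 90% power with 16,000 per arm, for an assumed certain-arm rate of 2.0% to 3.0%.
3. Report 97.5% intervals for the two primary contrasts, so that interval and test agree.

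The cost is a few sentences of text and one further analysis of data already collected. The primary intervals become about 14% wider. Sample size and Aim 1 power do not change.

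### The two primary contrasts are tested at two-sided 0.025 but reported with 95% intervals, so the intervals lack the multiplicity adjustment that the tests carry

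*Protocol*

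**What the plan says.** Three statements in the Protocol bear on this.

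- **Sample size determination (5b).** The power calculation uses a two-sided chi-square comparison of an incentive arm with control. The level is fixed in these words: "assuming a type I error rate of 2.5% (to account for the two hypotheses of interest"). The reduced level is therefore a deliberate allowance for having two incentive arms.
- **Statistical Analysis (5c), number of contrasts.** "Separate analyses will be conducted for each financial incentive intervention arm against the active control arm". There are two primary contrasts with a shared control.
- **Statistical Analysis (5c), reporting and testing.** "All results will be reported as point estimates (e.g., percentage difference between groups) and interval estimates (two-sided 95% confidence intervals"). The sentence that follows says that tests of each incentive arm against control "will be conducted at a two-sided alpha level of 0.025".

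The interval level is set for every result. The primary contrasts are not excepted, and the 95% intervals are not described as unadjusted or descriptive.

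**The concern.** A two-sided test at level alpha and a two-sided interval at level 1 − alpha are two views of one calculation: the test rejects exactly when the interval excludes no difference. The counterpart of a 0.025 test is a 97.5% interval. A 95% interval is the counterpart of a 0.05 test, which is the level the plan gave up when it allowed for two hypotheses.

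The enrollment difference with its interval will be the headline result. If a primary p-value lands between 0.025 and 0.05, the report will show an interval that excludes zero beside a test that is not significant. A reader who judges by the interval applies 0.05 to each contrast. The conflict runs one way only: when interval and test use the same statistic, the 95% interval can exclude no difference while the test fails to reject, never the reverse.

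**Working it through.** **Inputs, all from the Protocol**

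- "With a sample size of 16,000 members in each treatment arm (48,000 overall")
- "assuming an enrollment rate of 2% in the active control arm"
- "we have 90% power to detect an absolute difference of 0.59% or higher", that is, 2.59% against 2%
- Test level two-sided 0.025 per contrast, two contrasts; interval level 95%

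**1. Reproduce the stated power**

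Power = Φ{[d − z·√(2p̄(1−p̄)/n)] / √[(p1(1−p1) + p2(1−p2))/n]}, with p1 = 0.02, p2 = 0.0259, p̄ = 0.02295, n = 16,000 and z = 2.241.

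- Null standard error: √(2 × 0.02295 × 0.97705 / 16,000) = 0.001674
- Alternative standard error: √[(0.0196 + 0.02523)/16,000] = 0.001674
- Power = Φ[(0.0059 − 2.241 × 0.001674)/0.001674] = Φ(1.283) = 90.0%

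This matches the stated 90%. At two-sided 0.05 the power would be 94.1%, so the trial was sized on two-sided 0.025.

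**2. Width**

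The critical values are 1.960 for 95% and 2.241 for 97.5%. The ratio is 2.241/1.960 = 1.144, so the matching interval is about 14% wider.

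**3. Where interval and test disagree**

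Take 320/16,000 (2.00%) enrolled in control. The test is the pooled z (chi-square) of the power section. The interval is d ± z·√[p1(1−p1)/n + p2(1−p2)/n]. Differences and limits are in percentage points.

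| Enrolled, incentive arm | Difference | z | p | 95% lower limit | 97.5% lower limit | Test at 0.025 |
|---|---|---|---|---|---|---|
| 370 | 0.313 | 1.924 | 0.0543 | −0.0058 | −0.0515 | does not reject |
| 371 | 0.319 | 1.961 | 0.0498 | 0.0003 | −0.0455 | does not reject |
| 378 | 0.363 | 2.220 | 0.0264 | 0.0424 | −0.0035 | does not reject |
| 379 | 0.369 | 2.256 | 0.0240 | 0.0485 | 0.0025 | rejects |

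From 371 to 378 the 95% interval lies above zero and the test does not reject. The 97.5% interval first excludes zero at 379, where the test first rejects.

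**4. How often, per contrast**

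The chance of conflict is P(reject at 0.05) − P(reject at 0.025).

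- No true effect: 5.0% − 2.5% = 2.5%, of which 1.25% favours the incentive
- True rate 2.30%: 45.6% − 34.8% = 10.8%
- True rate 2.35%: 57.4% − 46.2% = 11.2%
- True rate 2.40%: 68.4% − 57.8% = 10.6%
- Design effect, 2.59%: 94.1% − 90.0% = 4.1%

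The maximum is about 11.2%. The band from 1.960 to 2.241 has half-width 0.141, and 2Φ(0.141) − 1 ≈ 0.112.

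**5. The pair of intervals together**

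Under equal rates and equal arms, each difference has variance 2σ²/n. The two differences share the control variance σ²/n, so their correlation is (σ²/n)/(2σ²/n) = 0.5. From the bivariate normal:

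- Two 95% intervals: joint coverage 90.9%, so at least one misses 9.1% of the time (9.75% if independent, bound 10%)
- Two 97.5% intervals: joint coverage 95.4%, so at least one misses 4.6% of the time (4.9% if independent, bound 5%)

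**The case against.** The strongest reply is that the plan's allowance for two hypotheses concerns tests, and the tests honour it. The only stated decision rule is the 0.025 test, so the error rate of the formal conclusions and the power stand. A 95% interval labelled 95% has its nominal coverage for each contrast taken alone, and showing unadjusted intervals beside adjusted tests is a recognised practice. The band of conflict is also narrow: eight possible counts in the example, and the 11% applies near a true effect of little more than half the one the trial is powered for.

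All of that stands, and it limits the point to reporting. It does not remove the point. The practice is defensible when the intervals are labelled as unadjusted, and here they are not. Nor is this a detail left to a statistical analysis plan, because the Protocol itself states both levels and they do not match.

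A reader might infer more than the document supports:

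- **That the trial's type I error is inflated.** It is not; the test decides.
- **That the Protocol promises 5% simultaneous coverage and breaks the promise.** It never states a 5% family-wise rate or makes an interval a criterion for success. The 5% follows only from 2 × 0.025, and it concerns tests.
- **That the percentage difference is the wrong companion to an adjusted logistic test.** The Protocol gives that measure only as an example, and its derivation may properly be settled in the analysis plan.
- **That the joint-coverage argument covers the secondary outcomes.** The Protocol leaves them without further adjustment for multiplicity, so it does not carry over to them.

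**Conclusion.** The stated interval level does not match the stated test level for the two primary contrasts, and the wording should be corrected. The consequence is a possible visible contradiction between interval and test. Its probability per contrast is 2.5% under no effect (1.25% in the incentive's favour), at most about 11% near a true increase of 0.35 points, and 4.1% at the design effect. Joint coverage of the reported pair is about 91% instead of about 95%. The pre-specified decision, the type I error and the 90% power are not affected.

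These figures assume 16,000 per arm, 2% control enrollment and normal approximations for unadjusted proportions. The planned test comes from an adjusted logistic model, so the exact counts at which conflict occurs may shift slightly. The mismatch between a 0.025 test and a 95% interval does not depend on that model. The joint-coverage figures also assume a correlation of 0.5; under independence they would be 90.25% and 95.1%.

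**What to change.** In the Statistical Analysis section, except the two primary incentive-versus-control contrasts from the general 95% rule and report them with two-sided 97.5% confidence intervals. If 95% intervals are also shown for these contrasts, for instance for comparison with other studies, label them as unadjusted for multiplicity and not used for inference.

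The cost is about one sentence of text and primary intervals about 14% wider. Sample size, power, data collection and the decision rule stay as they are. The change should be made before results are seen, so that the interval level is not chosen after the fact.
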